2. OBJECTIVES

2.1. Primary Objective

- Evaluate the safety and tolerability of single- and multiple-ascending doses of ALN-GO1, respectively, in healthy adult subjects and in patients with PH1

2.2. Secondary Objectives

- Characterize the PK of ALN-GO1
- Evaluate the PD of ALN-GO1

2.3. Exploratory Objectives

- [REDACTED] exploratory [REDACTED]
- [REDACTED]

3. ENDPOINTS

3.1. Primary Endpoint

- The primary endpoint is the incidence of adverse events (AEs). Safety will also be evaluated through vital signs, electrocardiograms (ECGs), clinical laboratory assessments, and physical examinations.

3.2. Secondary Endpoints

3.2.1. Secondary Endpoints for the Single-ascending Dose Part in Healthy Adult Subjects (Part A)

- PK parameters including, but not limited to, maximum plasma concentration [C_{max}], time to reach maximum plasma concentration [t_{max}], area under the plasma concentration versus time curve [AUC], apparent terminal elimination half-life [$t_{1/2}$], fraction eliminated in urine [f_e/F], and renal clearance [CL_R]
- Plasma and urine glycolate concentration

3.2.2. Secondary Endpoints for the Multiple-ascending Dose Part in Patients with Primary Hyperoxaluria Type 1 (Part B)

- PK parameters including, but not limited to, C_{max} , t_{max} , AUC, $t_{1/2}$, f_e/F , and CL_R
- Urinary oxalate excretion (oxalate concentration in 24-hour urine collection)
- Urinary glycolate excretion (glycolate concentration in 24-hour urine collection)
- Plasma glycolate concentration
- Calculated creatinine clearance

3.3. Exploratory Endpoints

- Plasma oxalate concentration
- [REDACTED]

3.3.1. Exploratory Endpoints for the Multiple-ascending Dose Part in Patients with Primary Hyperoxaluria Type 1 (Part B)

- [REDACTED]
- [REDACTED]
- [REDACTED]

4. INVESTIGATIONAL PLAN

4.1. Summary of Study Design

This is a randomized, single-blind, placebo-controlled study of subcutaneously administered ALN-GO1. The study is designed to evaluate the safety, tolerability, PK, and PD of single- and multiple-ascending doses of ALN-GO1 and will be conducted in 2 parts:

[figure not shown]
- Part A: single-ascending dose (SAD) part in healthy adult subjects
- Part B: multiple-ascending dose (MAD) part in adult and pediatric patients with PH1

The study will be conducted in a single-blind manner, with the Investigators, SRC, and Sponsor unblinded to permit ongoing unblinded review of safety, tolerability, PK, and PD data.

Part A will be conducted at 1 clinical study center in the UK. Part B is expected to take place at approximately 12 clinical study centers worldwide.

The study design is summarized in [Figure 1](#).

Figure 1: Study Design

^a Patients in Part B will be invited to participate in an open-label extension study once they complete the postdose follow-up period. For patients who do not enter the open-label extension study, safety and PD follow-up will continue until they meet the criteria described in Section 4.1.2, or until the SRC makes a decision per investigator request to discontinue follow-up on a case-by-case basis. The decision cannot be made until after completion of the last postdose follow-up visit (84 days after last dose).

4.1.1. Single-ascending Dose Part in Healthy Adult Subjects (Part A)

Part A is the single-ascending dose part of the study in healthy adult subjects. Subjects will be enrolled in 1 of 3 ascending dose cohorts, with the possibility for 2 additional optional cohorts. Each cohort will be comprised of 8 subjects randomized 3:1 to ALN-GO1 or placebo (study drug).

Subjects will be screened from -45 to -2 days before study drug administration. Subjects will be admitted to the clinical study center on Day -1 to determine continued eligibility and for predose assessments. Subjects in each cohort will be randomized on Day 1 and will receive 1 SC dose of

study drug. Subjects will be discharged from the clinical study center on Day 2 after completing the 24-hour postdose follow-up assessments.

Subjects will return to the clinical study center on an outpatient basis for safety, tolerability, PK, and PD monitoring at time points specified in the Schedule of Assessments through the last postdose follow-up visit (Day 57). Safety and PD follow-up will continue: 1) for at least 57 days, and 2) until plasma glycolate decreases to a level that is no more than 20% above of baseline or until plasma glycolate is below the upper limit of normal (≤ 14 nmol/mL).

4.1.2. Multiple-ascending Dose Part in Patients with Primary Hyperoxaluria Type 1 (Part B)

Part B is the multiple-ascending dose part of the study in up to 24 adult and pediatric patients with PH1 with relatively well-preserved renal function. Two ascending dose cohorts will be enrolled, with the possibility to also enroll up to 3 additional optional cohorts to further explore the optimal dose or regimen. Each cohort will be comprised of 4 patients, randomized 3:1 to ALN-GO1 or placebo. Up to 2 cohorts in Part B may be expanded by up to 4 additional patients per cohort (these patients will all receive ALN-GO1, not placebo).

Patients will be screened within 45 days prior to study drug administration. Baseline urinary oxalate excretion and creatinine clearance will be assessed through 24-hour urine collections. Patients will be randomized between Day -1 and Day 1 and will receive the first dose of ALN-GO1 or placebo on Day 1. The 24- and 48-hour postdose follow up assessments will take place on Day 2 and Day 3. Patients who receive study drug monthly will return to the clinical study center for safety, tolerability, PK, and PD monitoring at time points specified in the Schedule of Assessments (Table 2) for the remaining 2 single-blind doses of study drug (through Day 57). After completion of the blinded portion of the study, patients dosed monthly will be unblinded (on or after Day 78). Patients who initially received placebo will then receive ALN-GO1 at the same dose administered to the cohort into which they were initially randomized and will follow the same assessment schedule as indicated in Table 3.

Patients who receive study drug quarterly will return to the clinical study center for safety, tolerability, PK, and PD monitoring at time points specified in the Schedule of Assessments (Table 4) and will receive a 2nd dose of study drug at Day 85. Patients who initially received placebo will receive a single dose of ALN-GO1 on Day 85 at the same dose administered to the cohort into which they were initially randomized. Patients dosed quarterly will be unblinded to initial treatment assignment following completion of the postdose follow-up period.

After the dosing period, patients will return to the clinical study center for continued safety, tolerability, PK, and PD monitoring for at least 12 weeks (84 days) following the last dose of study drug. Following completion of the 12-week postdose follow-up period, patients will be invited to participate in an open-label extension study.

For patients who do not enroll in the open-label extension study, safety and PD follow up will continue until 24-hour urinary oxalate is $>80\%$ of baseline, and plasma glycolate is $<20\%$ above baseline or \leq the ULN. If an investigator wishes to discontinue follow up after completion of the postdose follow-up period and prior to oxalate and glycolate recovery, the SRC must agree based upon consideration of emerging data on the safety of ALN-GO1 knockdown and the individual patient's safety and PD data.

4.2. Duration of Treatment and Overall Duration of Study

The duration of treatment is as follows:

- Part A: The estimated total time on study, inclusive of screening, for each subject is up to 405 days. The duration of treatment is a single dose.
- Part B: For all patients, the duration of screening is up to 45 days and the minimum duration of postdose follow-up is 84 days. The duration of treatment and estimated total time on study, inclusive of screening, for each patient is as follows:
 - For patients dosed monthly: The duration of treatment for patients initially randomized to receive active study drug is 57 days. The estimated total time on study is up to 462 days. Additionally, the duration of treatment for patients initially randomized to receive placebo is 141 days. The estimated total time on study for each patient initially randomized to receive placebo, then active study drug, is up to 546 days.
 - For patients dosed quarterly: The duration of treatment is 85 days for patients randomized to placebo and active study drug. The estimated total time on study is up to 490 days.

The overall duration of the study is estimated to be 4 years, including enrollment.

4.3. Number of Subjects and Patients

A total of up to 64 participants (including optional and expansion cohorts) are planned to be enrolled in this study as follows:

- Part A: Up to 40 healthy adult subjects
- Part B: Up to 24 adult and pediatric patients with PH1

4.4. Method of Assigning Patients to Treatment Groups

This is a randomized, single-blind, placebo-controlled study. In Parts A and B, after confirmation of eligibility, during screening, and upon admission to the clinical study center, subjects/patients will be assigned to a dose level cohort and randomized in a 3:1 ratio (ALN-GO1:placebo). No subject/patient will be a member of more than 1 cohort. A unique subject/patient identification number, incorporating the clinical study center number, will be assigned sequentially to the subject/patient.

The clinical study center pharmacy staff will randomize the subject/patient in accordance to a cohort-specific randomization list generated by the biostatistician at the Contract Research Organization (CRO), for appropriate dispensation of the study drug.

The information furnished to the Sponsor for subject/patient identification will be the assigned subject/patient identification number, the randomization number of subjects/patients admitted to the study, the age, and sex. The subject's/patient's identification number will appear on all documents relating to that subject/patient and will be cross-referenced by the randomization number for the enrolled subjects/patients. The Sponsor may receive a copy of the randomization list.

4.5. Blinding

This is a single-blind, placebo-controlled study; therefore, only the study subjects/patients will be blinded to treatment assignment. Patients in Part B dosed monthly will be unblinded on or after Day 78 in order for patients and their families to be better prepared for the transition to receive ALN-GO1 if initially randomized to placebo. Patients dosed quarterly will be unblinded to initial treatment assignment following completion of the postdose follow-up period. The Investigators, Medical Monitors at the Sponsor and CRO, clinical study center personnel, pharmacokineticist, and members of the SRC will have knowledge of the treatment assignment. The clinical study center pharmacy staff will maintain the single-blind according to clinical study center-specific procedures and the Pharmacy Manual. Syringes containing dispensed study drug will be masked in the pharmacy before transfer to the clinic.

During the blinded period, if the subject/patient becomes seriously ill during the study, and the treating physician determines that the clinical management of the subject requires that the subject know the study drug assignment, the Investigator may break the blind, as necessary. If time permits, clinical study center personnel should contact the Medical Monitor before unblinding to discuss the need to unblind the subject/patient. A record of when the blind was broken, who broke the blind, and why it was broken, will be maintained in the Trial Master File.

See the Pharmacy Manual for additional details.

4.6. Safety Review Committee

A SRC will perform ongoing reviews of safety, tolerability, and available study data collected in all study parts (Parts A and B) with the primary purpose of protecting the safety of subjects/patients participating in this clinical study. The SRC will undertake safety data review before initiation of dosing in a new cohort in Part A and Part B, and before initiation of dosing in Part B. After initiation of dosing in Part B, safety reviews will be conducted in accordance with the SRC charter at a minimum of every 3 months for the duration of the study. Part A and Part B of the study will incorporate adaptive study design features, which will allow for the continuing modification of dosing options and/or regimen as new data emerge, and in accordance with recommendations of the SRC (Table 9). Protocol-defined stopping rules will be used as criteria for stopping cohorts (Table 6) or individual patients (Table 7). Additionally, the SRC may recommend discontinuation of the study at its discretion. The investigator may also request that the SRC determine on a case-by-case basis whether study follow-up will be discontinued in patients in Part B who do not enroll in the open-label extension study who have completed the postdose-follow up period, but have not yet met the recovery criteria for plasma glycolate and urinary oxalate specified in Section 4.1.2. The decision will be informed by emerging data on the safety of ALN-GO1 knockdown and the individual patient's safety and PD data.

The SRC will be comprised of the Sponsor Medical Monitor, a Medical Monitor from the CRO, the Principal Investigator from the clinical study center conducting Part A of the study, an independent pediatrician experienced in clinical investigation who is not a study Investigator, and 3 Investigators at the clinical study sites who will be selected by the Sponsor.

The SRC will be governed by a charter that will be signed prior to enrollment of the first subject.

4.7. Study Drug Dosing, Study Progression, and Dose Escalation

For the purpose of this study, progression rules are based on toxicity. The Common Terminology Criteria for Adverse Events (CTCAE; Version 4.0, or higher) will be used to grade AEs. The decision to enroll an optional cohort or extend an existing cohort will be made by the SRC based on available safety, tolerability, and PD data, if further elucidation of dose response is considered necessary to better understand dose response and/or safety and tolerability.

4.7.1. Study Drug Dosing, Study Progression, and Dose Escalation in Part A

The following are the planned dose levels for Part A; however, the actual dose administered may be modified based on SRC review of emerging safety, tolerability, and available PD data in previous cohorts. The initial starting dose level is expected to have an adequate safety margin and a low level of pharmacologic activity based on GLP toxicology study results and nonclinical pharmacology.

- Cohort 1: 0.3 mg/kg
- Cohort 2: 1.0 mg/kg
- Cohort 3: 3.0 mg/kg
- Cohort (optional)
- Cohort (optional)

The SRC will review a minimum of 48 hours of safety data from at least 6 subjects before escalation to the next dose level. The SRC will review AEs and clinical laboratory evaluation data in order to proceed to the next cohort.

Based on SRC review of accumulated safety and PD data, 2 additional optional subject cohorts may be enrolled and dosed according to the same eligibility criteria and randomization scheme as Cohorts 1 to 3. The additional cohorts may be enrolled at higher, lower, or intermediate dose levels, but will not exceed the maximum administered dose of 6.0 mg/kg.

4.7.2. Study Drug Dosing, Study Progression, and Dose Escalation in Part B

Preliminary safety and PD data from Part A was evaluated by the SRC. The initial dose level of 1.0 mg/kg for administration in Part B was shown to be well-tolerated, and the lowest pharmacologically active dose. In Part B, all patients in a cohort dosed monthly will receive the same dose for each of the 3 study drug doses. Patients initially receiving 3 doses of placebo will receive 3 doses of ALN-GO1, with all 3 doses being the same for each of the 3 administrations of ALN-GO1. Patients in a cohort dosed quarterly who are randomized to ALN-GO1 will receive the same dose for each of the 2 study drug doses. Patients initially receiving 1 dose of placebo on Day 1 will receive 1 dose of ALN-GO1 on study Day 85. The maximum dose administered will not exceed 6.0 mg/kg.

Dose levels and/or dosing regimen in each cohort in Part B may be modified by the SRC. The next higher dose cohort can be enrolled after at least 3 patients in the previous cohort receive their first and second dose and have been followed for at least 14 days following the second dose of study drug. The SRC must review accumulating safety data from both single- and multiple-ascending dose cohorts to confirm the dose level and permit dosing in the next MAD cohort. In

Part B, patients randomized to placebo will be administered active ALN-GO1 in an open-label manner according to the same dose and assessment schedule for the cohort to which they were initially assigned.

Based on SRC review of accumulated safety, tolerability, and PD data, 3 additional cohorts may be enrolled and dosed according to the same eligibility criteria in Part B to better define safety or PD effects. Additional cohorts may be enrolled at higher, lower, or intermediate dose levels, but will not exceed the maximum administered dose of 6.0 mg/kg, and will follow the protocol-specified dose escalation criteria.

Based on SRC review of accumulated safety, tolerability, and available PD data, up to 2 cohorts in Part B may be extended by up to 4 additional patients per cohort based on study progression and stopping rules. These patients will all receive active drug, not placebo.

4.7.3. Dose Suspension and Stopping Rules

For the purpose of this study, dose suspension and stopping rules are based on toxicity. Standard toxicity grading according to the CTCAE will be used to grade AEs. The term ‘suspension’ means that no further study drug will be administered at the dose level and that further dose escalation/progression will be suspended. If a suspension/stopping rule is met, there will be no further enrollment or dosing in the current cohort, or escalation to another cohort, in that part of the study and an ad hoc SRC meeting will be held. Following SRC review and recommendations, dosing may be resumed at the same or higher dose level following approval from the concerned Regulatory Authority and the independent ethics committee (IEC)/institutional review board (IRB), if required by local regulations. However, de-escalation to a lower dose or intermediate may be allowed without prior Regulatory Authority or IEC/IRB approval.

4.7.3.1. Cohort Progression/Escalation and Suspension/Stopping Rules in Part A

Study cohort progression/escalation and suspension/stopping rules for AEs considered possibly or definitely related to study drug for Part A are described in [Table 6](#). If a subject meets a stopping rule, the subject will be managed as clinically indicated and asked to complete all safety assessments according to the protocol.

Table 6: Cohort Progression/Escalation and Suspension/Stopping Rules for Part A

CTCAE Grade ^a	Severity/Seriousness	Reversibility	Number of Subjects Affected	Action	Effect on Dose Progression/Escalation
I	Mild	N/A	N/A		
II	Moderate	Showing signs of reversibility (ie, AE which shows signs of improvement in the judgment of Investigator)	≤2 subjects in different SOC	Next dose determined by SRC	N/A
			≤2 subjects in same SOC OR 3 subjects in different SOC ^b	Dose level may continue OR be extended AND dose escalation on hold until results of continuation or extension are available	Following continuation or extension, dose escalation may proceed as per clinical study protocol
			≥3 subjects in same SOC OR ≥4 subjects in different SOC ^b	Dose level suspended	A lower (intermediate) dose level may be administered in the next cohort AND dose continuation, extension, or escalation requires Regulatory Agency, IEC/IRB, and SRC approval
		Showing no signs of reversibility	≥2 subjects ^b		

Table 6: Cohort Progression/Escalation and Suspension/Stopping Rules for Part A

CTCAE Grade ^a	Severity/Seriousness	Reversibility	Number of Subjects Affected	Action	Effect on Dose Progression/Escalation
III	Severe, not serious	Showing signs of reversibility (ie, AE which shows signs of improvement in the judgment of Investigator)	1 subject ^b	Dose level may continue OR be extended AND dose escalation on-hold until results of continuation or extension are available	Following continuation or expansion, dose escalation may proceed as per the clinical study protocol
			≥2 subjects ^b	Dose level suspended	A lower (intermediate) dose level may be administered in the next cohort AND dose continuation, extension or escalation requires Regulatory Agency, IEC/IRB, and SRC approval
	Showing no signs of reversibility	≥1 subject			
	Severe, serious	N/A			
IV/V	Life-threatening/ Fatal	N/A	≥1 subject	Study suspended	Study continuation requires Regulatory Agency, IEC/IRB, and SRC approval

Abbreviations: AEs=adverse events; IEC=Independent Ethics Committee; IRB=Institutional Review Board; N/A=not applicable; SOC=System, Organ, Class; SRC=Safety Review Committee.

a Common Terminology Criteria for Adverse Events, Version 4.0 or higher, will be used to grade AEs.

b SRC review of Part A cohorts for escalation to the next dose level will occur following at least 48 hours of safety monitoring after the prior cohort has been dosed.

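### Table 6 (Part A): a single reversible related Grade II event meets two rows with different actions, and a single non-reversible one meets no row

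*Protocol*

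**What the plan says.** Protocol Section 4.7.3.1 states its scope as "rules for AEs considered possibly or definitely related to study drug for Part A are described in" Table 6. For Grade II events showing signs of reversibility the table has three rows:

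- Row 1: "≤2 subjects in different SOC". Action: "Next dose determined by SRC". The effect on escalation is given as not applicable.
- Row 2: at most two "subjects in same SOC OR 3 subjects in different SOC". Action: "Dose level may continue OR be extended AND dose escalation on hold until results of continuation or extension are available". Afterwards escalation may go ahead under the protocol.
- Row 3: "≥3 subjects in same SOC OR ≥4 subjects in different SOC". Action: the dose level is suspended.

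For Grade II events "Showing no signs of reversibility" there is one row, and its only count is two or more subjects. For Grade III events that are severe but not serious, the reversible rows start at one subject and the non-reversible row at one or more.

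Footnote b concerns only the 48-hour minimum of safety monitoring before SRC review. Section 4.6 makes the protocol-defined rules, including Table 6, the criteria for stopping cohorts. Table 9 requires the Section 4.7 minimum requirements to be met before progression or escalation.

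**The concern.** A decision table for first-in-human escalation should send each possible observation to one action. Here the smallest Grade II observation, one affected subject, does not get one. If the event is reversible, one row gives the SRC discretion over the next dose while the other requires a hold on escalation. If it is not reversible, the table is silent. Read literally, the table attaches a possible hold to one reversible event and no stated consequence to one non-reversible event of the same grade.

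The rule can still come into use. Section 4.7.1 and Table 9 allow two optional Part A cohorts at doses up to 6.0 mg/kg, above the highest planned Part A level of 3.0 mg/kg. Table 9 also caps Part B doses at levels judged safe and tolerable in Part A, so the Part A decisions carry over to patients.

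**Working it through.** **Inputs.** The Grade II counts and actions come from Table 6. The cohort size of 8, randomized 3:1 (6 active, 2 placebo), comes from Section 4.1.1. The plan states no figure to reproduce, and its sample size does not rest on a power calculation (Section 8.1).

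**Step 1: enumerate the Grade II cases.** Let n be the number of affected subjects, from 1 to 8. For n = 2 to 8 take two SOC patterns, all in the same SOC or all in different SOCs. For n = 1 there is only one pattern. That gives 1 + 7 × 2 = 15 cases per reversibility state, and 2 × 15 = 30 in all.

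| Case | Rows matched | Action |
|---|---|---|
| Reversible, n = 1 | **2** (rows 1 and 2) | SRC sets next dose; or escalation on hold |
| Reversible, n = 2, different SOCs | 1 (row 1) | SRC sets next dose |
| Reversible, n = 2, same SOC | 1 (row 2) | Escalation on hold |
| Reversible, n = 3, different SOCs | 1 (row 2) | Escalation on hold |
| Reversible, n = 3, same SOC | 1 (row 3) | Suspended |
| Reversible, n = 4 to 8, either pattern | 1 (row 3) | Suspended |
| Not reversible, n = 1 | **0** | None stated |
| Not reversible, n = 2 to 8, either pattern | 1 | Suspended (action cell apparently shared with row 3) |

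So 28 of the 30 cases match exactly one row. One matches two rows and one matches none. The split by SOC works at n = 2 and fails only at n = 1, where there is no second subject to compare. Mixed patterns, such as two subjects in one SOC and a third in another, were not enumerated, and the table does not address them either.

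**Step 2: look for a tie-break or default.** Sections 4.6, 4.7, 4.7.1 and 4.7.3 and footnote b were compared with the two failing cases. Section 4.7.1 has the SRC review adverse events and laboratory data before each new cohort. None of these places says which row governs one reversible event, or what follows one non-reversible event.

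**Step 3: how often n = 1 could arise (illustration only).** The documents give no event rate. Assume that each subject independently has probability p of a related Grade II event, with reversible and non-reversible events taken together. Then P(exactly 1) = m·p·(1 − p)^(m−1) and P(at least 1) = 1 − (1 − p)^m, with m = 6 (active only) or m = 8 (all subjects, at the same rate). For m = 6 and p = 0.10: 6 × 0.10 × 0.9⁵ = 0.354 and 1 − 0.9⁶ = 0.469, a share of 0.354 / 0.469 = 0.76.

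| Assumed p | P(exactly 1), m = 6 | Share of cohorts with any event, m = 6 | P(exactly 1), m = 8 | Share, m = 8 |
|---|---|---|---|---|
| 2% | 0.11 | 95% | 0.14 | 93% |
| 5% | 0.23 | 88% | 0.28 | 83% |
| 10% | 0.35 | 76% | 0.38 | 67% |
| 20% | 0.39 | 53% | 0.34 | 40% |
| 30% | 0.30 | 34% | 0.20 | 21% |

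The contradiction and the gap do not depend on these rates.

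**The case against.** The strongest reply is that nothing in Part A escalates automatically. Under Section 4.7.1 the SRC reviews adverse events and laboratory data before each new cohort and may change the dose. Under Section 4.1 it is unblinded, and under Section 4.6 it may recommend stopping the study at its discretion. This stands, and it limits the consequence: either kind of single event would still come before an informed committee. It does not supply the missing row or choose between the two that overlap.

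A second reply is that the two actions are not opposite orders. Row 1 does not direct escalation, and an SRC that chose to hold would satisfy both rows. This also stands. A reader might infer that one event leads to escalation under one row and a hold under the other, but the text supports only discretion against a required hold.

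A third reply is that one of the two upper bounds is probably loose drafting. That may be so, but the text does not say which, and the guess would not fill the non-reversible gap. Some cells of the table appear merged or shifted, so the layout is worth checking against the original. The point rests on the printed counts, not on the blank cells.

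Lastly, the future effect is limited. Part A data had already been used to set the Part B starting dose (Sections 1.4 and 4.7.2), Part B has its own Tables 7 and 8, and the optional Part A cohorts are allowed but not shown to be planned.

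**Conclusion.** The point holds for two cases: exactly one subject with a reversible related Grade II event (two rows, different actions) and exactly one with a non-reversible one (no row). This is an inconsistency inside a stated safety rule, not just missing detail.

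Three stronger readings are not supported:

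- That Table 6 as a whole cannot be applied. The other 28 enumerated Grade II cases map to one row, and the Grade III and Grade IV/V rules are not affected by this finding.
- That escalation could go unsupervised. The SRC reviews every Part A escalation.
- That a single Grade II event is the most likely trigger. That depends on rates the documents do not give. At an assumed 30% with 6 active subjects, exactly two affected (15 × 0.3² × 0.7⁴ = 0.32) is slightly more likely than exactly one (0.30).

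The conclusion assumes a literal reading of the printed counts and covers only patterns in which all affected subjects share one SOC or all differ.

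**What to change.** Reconcile the Grade II rows of Table 6 so that each combination of subject count, SOC pattern and reversibility state maps to exactly one row and one action. A single reversible event and a single non-reversible event should each be named, and mixed SOC patterns should be assigned at the same time. Which action applies is for the sponsor and the SRC to decide. The cost is a wording change to one table in an amendment, with no change to sample size, assessments or analysis. It should be in place before any optional Part A cohort is opened. If a cohort already dosed had exactly one related Grade II subject, the study report could record which row was followed.
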